# Session 1 – Introduction & Psychoeducation

## Script

### Introduction:

Hello and welcome to the first session of guided self-help for sexual distress. Over the next 4 sessions we hope to cultivate a more compassionate view towards yourself by deepening your understanding of yourself and your difficulties, and how your experience of sexual trauma is affecting your sex life and the it affects your mind and body.

We have based this information from scientific research and throughout the sessions, we will also be going through a range of exercises for you to practice and ask for you to note down any reflections you feel comfortable writing. You have the choice of which exercises you want to try and which you would prefer to opt out of. It is completely okay to step away from any of the exercises over the next 4 weeks, you do what feels right for you. Even choosing to sign up for this 4 week intervention is a big step and we hope that this guide will help you feel more confident in returning to sex and treat yourself with more kindness when approaching sex even if it feels like it may be difficult.

### Breathing exercise:

Breathing is a great form of mindfulness which cultivates our ability to be present in the moment. We will learn more about mindfulness in the next session. To help you prepare for today's session I would like to bring you to the present moment, let's get into a comfortable position and start by taking a deep breathe and relaxing any tension you may feel in your body. Take yourself away from any distractions and if you feel comfortable to do so. you can close your eyes and take a minute or two to allow your attention to settle on your breathing – not really thinking about anything in particular. Alternatively, or when you are ready, take one last deep breathe, stretch wiggle your finger and toes and bring yourself back in to the room.

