### How can mindfulness help after trauma?

Studies have found that mindfulness helps reduce distracting thoughts, increases focus on physical sensation, and is helpful for sexual difficulties. It helps us learn to be in the moment by being aware of our physical sensations. And we want to build on compassion and activate our soothing system which we can do through mindfulness.

However, some survivors of sexual trauma may find mindfulness difficult or triggering and dissociates. Mindfulness may be quite distressing if it means sitting with sensations and emotions that are usually avoided. and If your mind ‘shuts off’ during your experience of trauma, the feeling of ‘shutting off’ can occur again when you’re faced with similar or difficult emotions. If you experience these difficulties, it’s okay. It’s a protective mechanism to keep you safe. You can opt-out of the mindfulness exercise and practice being present in a different way. One way to do this is through everyday mindfulness.

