### Everyday Mindfulness

In any task we do, we can be mindful and present. Choose a routine task and each day for the next week; see if you can remember to pay attention while doing it. You do not have to slow it down or even enjoy it. Simply do what you normally do, but see if you can be fully alive to it as you do so.

Examples like: Brushing your teeth. Drinking a hot drink.

We are going to now have a short mindfulness practice – if you know mindfulness is difficult for you because of your experience of sexual trauma, you can skip the practice and I invite you

to do anything you find soothing or if you feel up for it, practice one of the everyday mindfulness activities instead. However, if you would like to give the activity a go, then continue and remember you have control and can stop and move on from this exercise at any point.

To begin, find a comfortable sitting position and if you feel comfortable, closing your eyes.

***Mindfulness Attention Practice – based on Paul Gilbert's exercise. From Compassionate-Mind Guide to Recovering from Trauma and PTSD Deborah A. Lee***

*“Sit quietly for a moment and focus on your breathing. Allow the breath to come down into your diaphragm slowly and evenly and then leave your body slowly and evenly. If you find this difficult you may simply want to try to focus on the sensation of your breath coming in and leaving through your nose. Try spending two minutes simply concentrating on the experience of breathing in and out. If you don’t like focusing on your breathing or you don’t like closing your eyes, you could use a pebble or a shell and try to focus your attention on the experience of looking at it and feeling it or look at a blank wall.*

*As you focus on your in breath and out breath You may notice that within just a few moments your mind will have wandered off on to something else. This is called mind wandering. If there are things that are worrying us, our minds easily get pulled into thinking about them and away from the present moment. This can also happen if there are things we are looking forward to (like a party), or if there are things that we need to do (e.g., pay a bill, or remember to call a friend), and we can find our minds skipping to them. This is very typical of how our minds are, and indeed recent research evidence suggests that it is our natural state.*

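### Session 1 opens with a breath-focus exercise that the manual calls mindfulness, but the manual's own caution for survivors and its other focus of attention first appear in session 2

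*Protocol*

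**What the plan says.** The intervention manual (the document titled Protocol) opens session 1 with a general permission to decline: "It is completely okay to step away from any of the exercises over the next 4 weeks". The breathing exercise follows directly. Its script introduces it with "Breathing is a great form of mindfulness which cultivates our ability to be present in the moment", and the core instruction is that "you can close your eyes and take a minute or two to allow your attention to settle on your breathing", with closing the eyes conditional on feeling comfortable. It ends: "Alternatively, or when you are ready, take one last deep breathe, stretch wiggle your finger and toes", and the participant returns her attention to the room. In the session 1 handout only the heading of this exercise is visible.

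Session 2, under *How can mindfulness help after trauma?*, states that "some survivors of sexual trauma may find mindfulness difficult or triggering and dissociates" and gives a reason: "Mindfulness may be quite distressing if it means sitting with sensations and emotions that are usually avoided". It then offers a way round: "You can opt-out of the mindfulness exercise and practice being present in a different way". Under *Everyday Mindfulness* it adds "remember you have control and can stop and move on from this exercise at any point". The guided practice there suggests a small object or a blank wall for anyone who does not want to focus on the breath or close her eyes. The session 2 handout repeats the warning about dissociation.

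The Combined protocol and SAP (2.1 and section 3) schedules one module per week, worked through online.

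**The concern.** The manual names a reaction that some survivors may have to mindfulness, and it supplies both a warning and a substitute. It does so only after a participant has already been led through an exercise that it calls mindfulness. A woman new to the practice has no reason, in session 1, to know that breath focus may be hard for her. A general opt-out helps less when she does not know what she might wish to avoid.

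What is at stake is participant safety, on a small scale. Section 3.4 of the Combined protocol and SAP describes crisis signposting at the start and end of each resource, and clinician triage on request. Section 2.2 describes a risk screen and a call. As described, none of these tells her that this exercise may be difficult or what she could attend to instead. She works alone, and section 2.2 says the chief investigator hears of increased risk only if she emails.

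**Working it through.** No figure in the plan depends on this point, so the check is a comparison of texts. All visible session 1 text, script and handout, was read for two things: a caution specific to mindfulness, and an alternative object of attention. The first place where each occurs in the manual was then located.

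| Element | Session 1 | Session 2 |
|---|---|---|
| Exercise called mindfulness | Yes, in *Breathing exercise* | Yes, in *Everyday Mindfulness* |
| General permission to decline | Yes, in *Introduction* | Yes, in the opening script |
| Eye closure conditional on comfort | Yes | Yes |
| Caution that mindfulness can distress survivors | None visible | Yes, script and handout |
| Other focus of attention | None visible | Yes: an object, a blank wall or an everyday task |
| Permission to stop midway, stated at the exercise | Only the loose exit that closes it | Yes, explicit |

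**Count of mentions.** The stem *mindful* occurs three times in the visible session 1 text: twice in the breathing exercise script and once as a handout heading (2 + 1 = 3). One of the script uses only announces the next session's topic. None of the three carries a caution. The count confirms absence; it does not measure exposure, which is one exercise.

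**The exit.** "Alternatively, or when you are ready, take one last deep breathe, stretch wiggle your finger and toes" could be read as offering movement in place of breath focus. However, the sentence goes straight to a final breath and the return to the room. It lets a participant finish early or pass over the exercise, but gives her nothing else to attend to meanwhile.

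**Duration and lag.** The exercise lasts one to two minutes. The visible *Week 1 Practice* does not repeat it. The caution follows one module later, which at one module per week is about seven days.

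**The manual's own pattern.** The main guided exercises in sessions 2, 3 and 4 each have their own opt-out directly beforehand, with something else to do: a soothing or everyday activity, something kind for oneself, or a few breaths or a drink. Session 1 is the exception. After its practice, session 2 tells a woman who found it hard that she may replace it from then on, which cannot reach back to session 1.

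**The case against.** The strongest reply is that this is a wording preference and most of the remedy is already present. The introduction lets a participant choose or step away from any exercise, which covers both skipping and stopping, and the comfort condition implies that open eyes are acceptable. The session 2 caution is conditional: it concerns staying with feelings that are usually avoided, and it precedes a longer practice and a week of daily audio. A short settling exercise is a different matter. Barts clinicians and experts by experience gave feedback on the materials (Combined protocol and SAP, 1.1, 2.3.1 and 2.4), so the order may be deliberate. The body of the handout exercise, the wording of the signposting and the participant information sheet cannot be seen, and any of them might carry the caution. A distress warning at the very start may also not be neutral for this group.

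Much of this stands. The opt-out and comfort condition are real safeguards, the sessions do not contradict each other, and keeping the full explanation in session 2 is reasonable. What remains is narrow. The manual itself labels the session 1 exercise mindfulness, itself names the hazard, and has no caution in the session 1 script, which is read out in a recorded video to women working alone. Review by clinicians and survivors does not show that the order was intended. Whether an early warning has a cost of its own is not settled by the documents, and is a reason to keep it short and have the same reviewers approve it.

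**Conclusion.** The point holds, as a minor one to consider. The first exposure to what the manual calls mindfulness comes without the caution and the substitute focus that the manual supplies about a week later. The extent is one optional exercise of one to two minutes, offered to every participant (minimum 6, target 20). No rate of adverse reaction is given in the documents and none is assumed here. Sample size, outcome measures and analysis are untouched.

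The conclusion rests on the visible text. The session 1 script can be read, but the handout exercise survives only as a heading, figures are missing, and the participant information sheet is not supplied. A caution in one of those places would leave the script as described and would reduce the change to repeating it at the exercise.

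**What to change.** Directly before the session 1 breathing exercise, in both script and handout, add two or three lines adapted from session 2. They should say that some survivors find mindfulness difficult or distressing, that it is fine to skip this or stop at any time, and that a participant may instead keep her eyes open and attend to an object, or do an everyday task. Leave the fuller account of dissociation in session 2. Ask the clinicians and experts by experience who reviewed the materials to approve the wording.

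The cost is a slightly longer opening, a short insert in one video and a small handout edit. Schedule, measures and analysis do not change.

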### Reflection:

To begin the session, I would like you to think about how you want to feel about your sex life and what about sex is important to you. Is it pleasure? Connection? Is not important to you. Take as much time as you need to reflect on this. If how you want to feel about your sex life is a 10 on a scale of 0 to 10, how close are you to feeling the way you want about your sex life?. What number would you rate your sex life currently from 0 to 10.

### How difficult experiences get in the way:

Research has shown how it is common and understandable for sexual trauma to affect someone's experiences of sex. For some people this changes the way they have sex or can lead to increased anxiety & fear of having sex and discomfort during sex. On the handout are a list of common experiences survivors of sexual trauma encounter when returning to sex. These experiences are understandable after trauma which is a violation of your safety and this is the way your brain is trying to protect you from being hurt again but it overcompensates, causing these symptoms. If you have any of these experiences currently, it is not your fault! You did not choose or want to react in these ways but our brains automatic response is to keep you safe.

The main task of all living things is survival and humans have evolved in many ways to detect and respond to threat to ensure we survive. The brain has also evolved to detect threat. The amygdala is the part of the brain that protects us from threat – it is the human built in threat alarm system. To protect us, the amygdala is constantly looking out for threat and lives by the rule ‘better safe than sorry’ so any small signs of danger can cause the alarm system to go off and our brain is told that we are in danger and prepares our body and mind to defend itself. This response occurs so quickly and automatically that sometimes it sets off our threat system before we are conscious of what is happening.

For example, if we are in a forest and see something moving on the ground we might feel scared and jump back before we realise it's a harmless bird. The role of the amygdala is to keep us safe and to react quickly before the thinking part of our brain identifies the movement as something that isn't dangerous.

Unfortunately, the amygdala is unable to distinguish between danger in the present from past events we remember in our minds. This is why the threat system may be activated when you have memories of trauma even if you rationally know you are in a safe place. Your brain is trying to keep you safe and prevent anything frightening from happening again. During the trauma, the amygdala collects information so that it can recognise warning signs in the future to prevent the event from occurring again. Anything that even vaguely reminds the amygdala of the original traumatic event, including the act of sex in a safe place on your own or with a trusted partner can trigger the threat system. When the ‘alarm system’ goes off because our threat system is triggered, it can interfere with the ability to have sex. I hope you will be reassured that many of the difficulties you experience are the results of the way the human brain is designed and to deal with threat.

The way our bodies respond sexually is related to a whole range of factors, many of which are outside our control such as the response of the threat system. One thing we can do to reduce the emphasis on the threat system is to activate our soothing system.

The soothing system is part of the three systems model and is linked to feelings of being safe and soothed. It is associated with being relaxed, connecting to others and experiencing compassion. Often for sex to be enjoyable we need : human connection, feeling safe, feeling wanted and our wishes respected. And a feeling of safety and no active threat. – these are all factors associated with the soothing system which is needed for arousal and enjoyable sex.

### Three Systems:

We have already introduced how the threat system can interfere during sex. We also briefly talked about how the soothing system is what makes us feel safe during sex allowing for arousal. These two systems, described above, are part of a three systems model. The third system is the drive system and it's involved in wanting and pursuing sex. From an evolutionary perspective, the principle aim of sex is reproduction. However, we know that is not everybody's drive for sex today.

After experiencing trauma, the threat system becomes more sensitive and is easily triggered, overruling the drive and soothing systems as your brain tries to protect you from being hurt again even if you are with a trusted partner. This may cause people to feel:

- unsafe, scared of sex etc.
- shame about what happened, disgusted with self or others.

- Some people worry that what happened to them was their fault, so might feel shame and feel undeserving of sex or closeness
- Might have critical thoughts like “I’m disgusting” or “I’m not worth it”

Our brains and bodies are not designed to have sex “perfectly” (e.g. in the way our **culture** currently says we should) … we’re evolved to survive...

It is understandable that if someone has had a threatening or unwanted sexual experience, sex might be experienced as threatening. A new sexual encounter might automatically trigger memories of the unwanted sexual experience **OR** sex drive might increase – as the brain’s way of managing the increased threat. This can be **automatic and unconscious**, and happen even if the person doesn’t want it to. The brain is doing what it thinks is helpful, even if it doesn’t feel helpful.

Building Compassion:

Over the next few weeks, we will work on acknowledging the difficulties and shame related to sex while building on the soothing system through different exercises. Increasing our soothing system will help increase our drive and alleviate the threat system. We do this by trying to be more compassionate with ourselves. This includes

- Understanding the way, we are and why we may act/feel this way – being wise about sex and our bodies
- Treating ourselves with warmth and kindness
- Being encouraging to ourselves
- Being non-judgmental about our experiences

Being compassionate will also allow us to be aware and engage with distress and difficulty without turning away from it and increase our motivation and courage to try to alleviate the distress.

Practice:

At the bottom of your handout there are some practice activities we encourage you to try throughout the week. It is perfectly okay to do all of them, some of them or none of them as long as you are doing what feels right for you. There is no pressure or need to be harsh with yourself if you were unable to incorporate these practices during the week, you are doing the best you can and being here for this first session is enough. Thank you for joining this week, this is a brief reminder to fill out the measures and questionnaires so that we can see how this intervention is helpful for survivors of sexual trauma. Thank you very much and I hope you found today’s session helpful, we will see you next week.

## Handout

### Aims of session 1

- To think about what you'd like from your sex life
- To understand the links between difficult experiences and sex
- To understand why our brains and bodies act the way they do
- To build compassion towards the ways our minds and bodies behave

### Mindful Breathing Exercise

#### Reflection: How would you like to feel about your sex life?

### How difficult experiences get in the way

- Difficult / traumatic experiences can affect experiences of sex
- For some people, this can lead to anxiety, fear, discomfort around sex, or change the way you have sex
- This is very understandable as our brains are programmed to protect us and keep us safe – it's not your fault!!!

## The brains alarm system

The amygdala is the part of the brain that protects us from threat – think of it as the brains alarm system. It is constantly looking out for threat and lives by the rule ‘better safe than sorry’ so any small signs of danger can cause the alarm system to go off and our brain is told that we are in danger and prepares our body and mind to defend itself. This responds occurs so quickly and automatically that sometimes it sets off our threat system before we are conscious of what is happening.

When this alarm system goes off because our  system is triggered, it can interfere with our ability to become aroused and enjoy sex.

What we need is to activate our  system. However, the way in which our bodies respond sexually is related to a whole range of factors – many of which are completely outside of our control.

- Human connection, feeling safe, feeling wanted and our wishes respected – basic human needs related to the **soothing** system
- A feeling of safety and no active threat

However, when you have experienced trauma, your body and brain tries to protect yourself from being hurt again even when are with a trusted partner.

## Sex & Emotions: Three Systems

We have already introduced how the **threat** system can interfere during sex. We also showed how the **soothing** system is what makes us feel safe during sex allowing for arousal, these two systems are part of the three systems model as seen above. The third system is the **drive** system and it's involved in wanting and pursuing sex. From an evolutionary perspective, the principle aim of sex is reproduction.

## Three Systems after Trauma

[figure not shown]
After experiencing trauma, the **threat** system becomes more sensitive and is easily triggered, overruling the **drive** and **soothing** systems. This causes people to feel

- unsafe, scared of sex etc.
- shame about what happened, disgusted with self or others.
- Some people worry that what happened to them was their fault, so might feel shame and feel undeserving of sex or closeness
- Might have self-blaming
- critical thoughts like “I’m disgusting” or “I’m not worth it”
- 

Our brains and bodies are not designed to have sex “perfectly” (e.g. in the way our **culture** currently says we should) ... we’re evolved to survive...

## A Compassionate Approach

Increasing our **soothing** system will help increase our **drive** and alleviate the **threat** system. We do this by trying to be more compassionate with ourselves. This includes

- Understanding the way, we are and why we may act/feel this way – being wise about sex and our bodies
- Treating ourselves with warmth and kindness
- Being encouraging to ourselves
- Being non-judgmental about our experiences

Being compassionate will also allow us to be aware and engage with distress & difficulty without turning away from it and increase our motivation and courage to try to alleviate the distress

